## 8. MEASUREMENT OF EFFECT

### Disease Control

Although disease control is not the primary endpoint of this trial, patients will be assessed by standard criteria for disease response with serum PSA and clinical examinations. For the purposes of this study, patients should undergo serum PSA and testosterone testing at baseline, 2 months (at start of RT), and every three to six months until completion of androgen manipulation at 2 years, 4 months according to the study calendar. After completion of study treatment, it is recommended that PSA should be drawn every 6 months until 5 years post-treatment. Clinical exams should be performed on a regular basis at the discretion of the treating physician, but at least biannually during the course of therapy and at least annually thereafter. Screening for distant metastases will be based on clinical information and is at the discretion of the treating physician.

## 9. STATISTICAL CONSIDERATIONS

### 9.1. Study Design/Primary Endpoint

The study is designed as a feasibility study to determine quality of life endpoints for men treated with oral androgen deprivation therapy in conjunction with dose-escalated radiation. Data gathered from this preliminary cohort will aid in defining the expected range of quality of life changes as to facilitate a subsequent Phase II randomized comparison of oral therapy with standard ADT.

The primary endpoint is HRQOL at 6 months after initiation of therapy; at this time point, symptoms and side effects are expected to stabilize. In a large study of HRQOL in patients treated with standard ADT, scores at 6 months were comparable to those at 24 months in all domains.[34] Analysis at the six month time point will allow an early evaluation of what is expected to persist during longer term follow-up. HRQOL will be summarized using a score reflecting reported symptoms in sexual, hormone/vitality, fatigue, and global quality of life domains. A composite score inclusive of each of these domains except for breast tenderness and gynecomastia will also be analyzed; assessments of breast tenderness and gynecomastia will be excluded from this summary score as it is expected that some patients may receive additional therapies directed at reducing this side effect which may confound the analysis. Incidence of breast symptoms and signs will be recorded and reported separately from the other HRQOL endpoints. Mean scores in each quality of life domain will be calculated and confidence intervals will be derived.

Quality of life and toxicity scores will be compared to those of patients in the synchronous control cohort receiving standard ADT with radiation. Univariate analysis of mean scores (continuous

variables) will be performed using a two sample t-test. Scores will also be compared between trial patients and the control cohort while controlling for covariates using linear regression analysis.

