### **4.2. Measuring Health-Related Quality of Life and Toxicity**

Patient-reported outcome measures will include a modified version of the Expanded Prostate Cancer Index Composite (EPIC-26) which has been validated as an alternative to the complete questionnaire (EPIC-50).[33] The questionnaire will include all EPIC-26 items as well as additional items in the hormonal/vitality domain drawn from the full length EPIC-50. General

health-related quality of life, including fatigue, will be assessed with the PROMIS v1.0 Global short form and the EQ-5D visual scale for quality of life. All items will be consolidated into 2 questionnaires. The first questionnaire is the standard questionnaire administered to all patients with prostate cancer in the department of radiation oncology (see Appendix A). A supplemental four page questionnaire will be administered to all patients on trial and to all consenting control patients at baseline (see Appendix B). Both questionnaires will again be administered at 1-2 months after initiation of hormonal treatment (before RT), at 3-4 months (during RT), and at 6 months after initiation of study therapy. Questionnaires will be completed in writing by the patient. Questionnaires at 12, 18, and 24 months after completion of radiation therapy will not be required, although any collected data over this time frame will be recorded and available for analysis.

The evaluation period of acute radiation-related toxicity will be defined by the period from the start of radiation to three months following the completion of radiation. Toxicity will be graded according to Radiation Therapy Oncology Group (RTOG) acute toxicity scale (see Appendix D). Toxicity will be recorded on a weekly basis during radiation treatment and at the first follow up visit. Chronic toxicities will also be graded according to the RTOG toxicity scale and will be recorded at each point of clinical contact beyond the third month after completion of radiation.

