#### **4.3. Experimental Controls**

Patients who meet eligibility criteria of the study but who do not enroll on the trial who receive standard ADT with radiation will be approached for participation in the parallel data collection study. These patients will serve as the control group with which to compare HRQOL outcomes of patients treated on trial. Patients consenting to enrollment on the parallel data collection study will receive standard of care treatment, follow-up, imaging, and laboratory studies not subject to the plan described in this protocol. Health information may be recorded from the electronic medical record. Patients on the data collection study will be asked to complete the same supplemental four-page questionnaire (see Appendix B) as those on trial at baseline, 1-2 months after initiation of standard ADT (before RT), and at 6 months. Completion of the supplemental questionnaire will not be required at 12, 18, and 24 months after initiation of radiation, however any collected data over this time frame will be recorded and available for analysis. In addition, all controls will complete the six-page questionnaire which is standard practice for all patients treated in the department of radiation oncology according to usual practice.

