# These labs will be drawn in the last week of radiation therapy

≠ Optional

Note that the protocol allows for 1 month of flexibility to meet any follow-up appointment time (e.g. the month 6 visit may occur at month 5 or month 7.)

Beyond month 10, follow-up is recommended but not required. All data collected between month 10 and month 28 will be registered under this study so that longer term quality of life data (beyond the primary endpoint of 6 months) may be analyzed.

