### **9.3. Analysis of Secondary Endpoints**

As secondary endpoints, the study will investigate oncologic outcomes of the prescribed protocol therapy including biochemical progression-free survival, distant metastasis-free survival, cause specific survival, and overall survival. Kaplan-Meier curves will be generated for each endpoint. Findings will be compared to a synchronous cohort of controls.

Biochemical progression free survival will be defined to be the time from the start of therapy with oral androgen manipulation until PSA failure occurs as defined by the Phoenix definition of a rise to 2 ng/ml above the nadir PSA value. The relative hazard for a PSA failure in patients on protocol therapy compared to those in the control cohort will be calculated using the proportional hazards regression model of Cox, but formal statistical conclusions will not be drawn from this analysis.

Hematologic effects of dual oral androgen manipulation will be assessed using hemoglobin levels from scheduled CBC's. Changes in mean hemoglobin between baseline and various time points throughout treatment will be assessed. Univariate analysis of mean scores will be performed using a two sample t-test.

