**The following questions are about your general health.**

List any health problems, including diagnosis of any other cancers, that have required new therapy (such as medicines or procedures) or hospitalization **since your last visit**:

List the date of any recent colonoscopy (examination of the colon using a camera): \_\_\_\_\_

List the date of any recent cystoscopy (examination of the bladder using a camera): \_\_\_\_\_

Include the names, addresses, and phone/fax numbers of any physicians who are actively involved with your medical care. We will send documentation of your clinic visit to any physicians listed here.

Physician use only	Grade	Comment
GI		
GU		
Sexual		
Other		

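### Section 9.1 compares toxicity with controls whose toxicity recording the protocol does not specify, so differences in ascertainment can bias the comparison

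*Combined protocol and SAP*

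**What the plan says.** **Trial patients.** Section 4.2 grades toxicity on the RTOG scale: "Toxicity will be recorded on a weekly basis during radiation treatment and at the first follow up visit". Late toxicity is graded on the same scale and "will be recorded at each point of clinical contact beyond the third month after completion of radiation". The calendar in section 7 shows toxicity assessment weekly during radiation and at months 6, 10, 16, 22 and 28. PSA is also on the calendar.

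**Controls.** Section 4.3 gives them "standard of care treatment, follow-up, imaging, and laboratory studies not subject to the plan described in this protocol". Only the supplemental questionnaire has set time points (baseline, 1-2 months and 6 months). Taking other health information from the electronic record is optional. The schema describes the cohort as a source of HRQOL data and does not mention toxicity or PSA.

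**Comparison.** Section 9.1 says "Quality of life and toxicity scores will be compared to those of patients in the synchronous control cohort receiving standard ADT with radiation", by two-sample t-test and by linear regression with covariates, and attaches no caveat to toxicity. For the oncologic endpoints section 9.3 says "Findings will be compared to a synchronous cohort of controls", with Kaplan-Meier curves and a Cox relative hazard for PSA failure. It adds that no formal conclusions will be drawn from the Cox analysis.

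**Existing form.** The departmental questionnaire in Appendix A has a box headed "Physician use only" with a grade column for GI, GU, sexual and other effects. It names no grading scale, and controls complete the form according to usual practice.

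**The concern.** Recorded toxicity depends on what happened to the patient and also on how often, and on what scale, someone looked. The plan fixes both for one cohort and leaves both open for the other. A difference in mean toxicity score could then reflect the recording process as well as the treatment. Covariate adjustment cannot repair this, because it works on the grades that were recorded and not on those that were missed.

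The plan gives no matched assessment windows, common grading procedure or sensitivity analysis. It also does not say how repeated weekly grades become one score per patient. If the score is the worst grade, it is especially sensitive to the number of assessments.

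The study is meant to inform a later randomized phase II comparison. A distorted toxicity contrast could be carried into the planning of that trial.

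**Working it through.** **The plan's own figure.** The only design figure is the 95% interval of plus or minus 15% for a success rate of 0.6 with n = 40 (section 9.2). The Wald half-width is 1.96 × √(0.6 × 0.4 / 40) = 0.152, so the figure is reproduced. It concerns single-arm HRQOL success, not toxicity or PSA. The documents give no toxicity rate, PSA failure rate or control visit interval. Every such input below is an assumption, shown as a range.

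**1. Capture by visit interval.** Suppose a toxicity episode lasts d weeks, starts at a uniformly random time over 8 weeks of radiation, and is graded only at visits k weeks apart. The chance that it is recorded is min(1, d/k). With one grading at the end of radiation it is d/8.

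| Grading during radiation | 1-week episode | 2-week episode |
|---|---|---|
| Weekly (trial cohort) | 100% | 100% |
| Every 2 weeks | 50% | 100% |
| Every 4 weeks | 25% | 50% |
| End of radiation only | 12.5% | 25% |

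If controls are also graded weekly, the rows are the same and there is no artefact.

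**2. Effect on the comparison.** Let the true rate p be equal in both cohorts, and let controls be captured at a fraction s of the trial cohort's capture. The spurious difference is p(1 − s) and the apparent risk ratio is 1/s.
- Smallest case, p = 0.20 and s = 0.9: 0.20 × 0.1 = 2 points, ratio 1.11.
- Middle case, p = 0.30 and s = 0.8: 0.30 × 0.2 = 6 points, ratio 1.25.
- Largest case, p = 0.50 and s = 0.5: 0.50 × 0.5 = 25 points, ratio 2.0.

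With 40 and 30 patients and a two-sided 5% test of proportions, the chance of a significant result against the trial cohort is about 4%, 8% and 57% in these cases. It would be 2.5% with equal capture.

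Section 9.1 plans a comparison of mean scores, not of proportions. If a missed episode is entered as grade 0 and capture does not depend on grade, the control mean is s times its true value. The proportional shortfall (10% to 50% here) is therefore the same. The power figures apply to proportions and are only a guide.

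**3. PSA.** A failure is dated at the test that finds it. With intervals L that fill 28 months, the mean delay is about ΣL²/(2 × 28).
- Trial calendar (months 2, 6, 10, 16, 22, 28): (4 + 16 + 16 + 36 + 36 + 36)/56 = 2.6 months.
- Assumed control schedules: 1.5 months for 3-monthly tests, 2.9 to 3.0 for 6-monthly and 5.4 to 5.5 for yearly.

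Simulation with equal true failure of 5% to 20% by month 28 gives an apparent trial/control rate ratio of 1.00 to 1.16. The top value occurs when the last control test is at month 24, so failures in months 24-28 are not found (28/24 = 1.17).

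Expected events run from 2 + 1.5 = 3.5 to 8 + 6 = 14. The 95% interval for the hazard ratio extends each way by a factor exp(1.96/√(D × 4/7 × 3/7)). This is 7.2 for D = 4 and 2.9 for D = 14. The possible PSA artefact is small beside that imprecision.

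**The case against.** The strongest reply is that the documents do not show controls being examined less often. Care outside the protocol plan is unspecified, which is not the same as sparser. Controls are treated with radiation as well, and they complete the departmental form that carries physician grade boxes. Their assessment may resemble the trial's. This stands. A reader might infer that there are fewer assessments in controls and a known bias against oral therapy, but the documents support only the possibility.

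A second reply is that the illustration is small beside the noise. In the middle case, 30% against 24%, the 95% half-width is 1.96 × √(0.30 × 0.70/40 + 0.24 × 0.76/30) = 0.21, against an artefact of 0.06. This also stands as a statement about significance. It does not remove a systematic error from an estimate that will be used to plan the next trial.

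Third, toxicity scores in 9.1 might partly mean patient-reported scores, because the schema uses the phrase just after describing questionnaire summaries. Section 4.2, however, defines toxicity by RTOG grade, so the ambiguity is a reason to clarify.

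Fourth, under-capture in controls could not create a false claim of benefit for oral therapy. The stopping rules in section 6.3 and the success rule in 9.2 use no control comparison. Both statements are correct and limit the severity.

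A reader might also infer that the PSA comparison is invalid. The documents do not support that: section 9.3 disclaims formal conclusions from the Cox model, and trial follow-up after month 10 is itself optional.

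**Conclusion.** The point holds for toxicity in a limited form. The plan fixes how toxicity is recorded in one cohort, leaves it open in the other, and compares the two without a caveat. Ascertainment can therefore bias the result, and neither size nor direction can be determined from the documents. Under-capture in controls would make oral therapy look more toxic, by 2 to 25 points over the assumed ranges. With equal capture the artefact is zero.

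The PSA part is minor. One gap remains there: section 9.3 starts biochemical progression-free survival at the start of oral androgen manipulation, which gives controls no time origin.

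A reader might infer that the primary endpoint is compromised. It is largely outside this point, because the supplemental questionnaire is scheduled at baseline, 1-2 months and 6 months in both cohorts. The sample size does not change. This is a worthwhile, inexpensive improvement and not a fatal flaw.

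**What to change.** - **Section 4.3 and Appendix A:** record the RTOG grade for consenting controls at their usual on-treatment visits during radiation and at first follow-up. Name the RTOG scale in the existing physician grade box. This adds no clinic visits.
- **Section 9.1:** say what a toxicity score is. Compare toxicity only over windows assessed in both cohorts: during radiation, first follow-up, and later windows where both have data. Report the number of assessments per patient in each cohort. If controls are not graded, label the toxicity comparison descriptive.
- **Section 9.3:** report PSA testing frequency by cohort and define the biochemical progression-free survival origin for controls as the start of ADT.
- **Separately,** reconcile section 4.6, which has patients followed on protocol to 2 years after radiation, with the calendar note: "Beyond month 10, follow-up is recommended but not required". Section 8 (PSA every three to six months to 2 years, 4 months) and the 2-year biochemical failure rule in section 6.3 both depend on that follow-up.

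Cost: protocol wording, modest data entry for about 30 controls, and the loss of some off-window trial data from the comparison.

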## SCHEMA

Patient Population: (see section 3.0 for complete eligibility criteria)

- Age  $\geq 70$  and/or Charlson Comorbidity Score  $\geq 2$
- Biopsy proven prostate adenocarcinoma
- No clinical or radiographic evidence of metastatic disease
- By risk groupings, 2+ intermediate risk factors or 1+ high risk factor
- Zubrod performance status  $\leq 2$
- No history of androgen deprivation therapy (ADT) [GnRH agonist or antiandrogen]
- No prior pelvic radiation

Required Sample Size: Minimum of 40 experimental subjects and 30 control subjects (total of 70).

Study Center:

University of Chicago Medical Center,.

Concept and Rationale: Randomized data support the addition of ADT to standard dose external beam radiation (RT) in men with non-metastatic, intermediate and high risk prostate cancer. However, the role of medical castration with ADT is less certain when dose-escalated RT is administered. In particular, the benefit of standard ADT remains unclear in older men and in those with medical comorbidities in whom the risks of therapy may be heightened. Therefore, we propose to de-intensify standard ADT in this population, in favor of dual oral androgen manipulation with an antiandrogen and a 5-alpha reductase inhibitor (5AR). We hypothesize that health-related quality of life (HRQOL) will be improved with the removal of the gonadotropin releasing hormone (GnRH) and that oncologic outcomes will not be compromised. Dual oral androgen manipulation therapy will be delivered prior to and concurrent with dose-escalated radiation with the goal of maximizing its anti-tumoral effect.

Primary Objective: To test the hypothesis that health-related quality of life (HRQOL) of men over 70 and/or with medical comorbidities treated with oral androgen manipulation and radiation (RT) will be improved compared to that of patients undergoing standard ADT and RT.

Secondary Objectives: To test the hypothesis that the oncologic outcomes of patients treated with dual oral androgen manipulation with RT will be comparable to the outcomes of patients undergoing standard ADT with RT.

Study Design: Single arm prospective, feasibility trial. A synchronous control cohort receiving standard ADT will be followed for collection of data on HRQOL endpoints.

Statistical Methods:

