Patient reported data will be grouped into summary scores in each relevant quality of life domain (sexual, urinary, bowel, hormonal/vitality). Quality of life and toxicity scores will be compared to those of patients in the synchronous control cohort receiving standard ADT with radiation. Univariate analysis of mean scores will be performed using a two sample t-test. Scores will also be compared between trial patients and the control cohort while controlling for covariates using linear regression analysis.

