## **1. OBJECTIVES**

### **1.1. Primary Objectives**

The broad objective is to test the feasibility of delivering dual oral androgen manipulation with an antiandrogen and a 5-alpha reductase (5AR) inhibitor in conjunction with dose-escalated radiation (RT) in intermediate and high risk prostate cancer patients 70 years of age or older and/or with moderate to severe medical comorbidities. The primary objective is to test the hypothesis that health-related quality of life (HRQOL) in patients treated with dual oral androgen manipulation will be improved compared to that of controls treated with standard androgen deprivation therapy (ADT) including a gonadotropin releasing hormone (GnRH) agonist +/- an antiandrogen.

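### The primary HRQOL comparison is with non-randomised controls, but the plan does not say whether the t-test or the regression answers it, which score is compared, or that baseline score is adjusted for

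*Combined protocol and SAP*

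**What the plan says.** Section 1.1 states the primary objective as a between-group hypothesis: HRQOL on dual oral therapy "will be improved compared to that of controls treated with standard androgen deprivation therapy (ADT"). The Schema says the same, and describes a single-arm trial with this addition: "A synchronous control cohort receiving standard ADT will be followed for collection of data on HRQOL endpoints". Section 4.3 defines who the controls are: "Patients who meet eligibility criteria of the study but who do not enroll on the trial who receive standard ADT with radiation". Group membership therefore follows from patient or physician choice.

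Section 9.1 fixes the time point: "The primary endpoint is HRQOL at 6 months after initiation of therapy". On content it says: "HRQOL will be summarized using a score reflecting reported symptoms in sexual, hormone/vitality, fatigue, and global quality of life domains", and adds a composite that leaves out breast tenderness and gynecomastia. For the comparison with controls, Section 9.1 gives two methods: "variables) will be performed using a two sample t-test. Scores will also be compared between trial patients and the control cohort while controlling for covariates". The first is univariate, on mean scores; the second is a linear regression. The Schema repeats both methods. Neither place labels one of them primary or lists a covariate.

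Baseline scores will exist in both groups. Section 4.2 says: "A supplemental four page questionnaire will be administered to all patients on trial and to all consenting control patients at baseline", and Section 4.3 schedules the same form for controls again at 6 months. In the statistical plan for HRQOL, baseline appears only in the success rule of Section 9.2 (a fall in the hormonal/vitality score of at most 30% from baseline). The sizing there is for the experimental group alone.

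**The concern.** Men who decline a trial designed to spare quality of life, or whose physicians prefer standard ADT, may start with different HRQOL from men who enrol. With unequal baselines, three analyses are compatible with the text: a t-test on 6-month scores, a t-test on changes, and a regression whose covariates are still open. They estimate different things and can disagree. Nothing says which one then answers the primary objective, and covariates could be chosen after the data are seen.

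At stake is the estimated HRQOL difference. Sections 2.2 and 9.1 intend these data to inform a later randomised phase II study, with quality of life as its primary endpoint, so a distorted difference would be carried into that design.

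**Working it through.** **The plan's own figure.** Section 9.2 gives n = 40, success rate 0.6 and a 95% interval of about 15 percentage points either side. Check: 1.96 × √(0.6 × 0.4 / 40) = 0.152. It reproduces, but it describes one proportion in one group and says nothing about the comparison with controls.

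**Inputs for the comparison.** From the documents: 40 and 30 patients. Assumed, because the documents give none of them: two-sided alpha 0.05, complete data, SD 1 at both times, within-group correlation ρ = 0.6 between baseline and 6 months (range 0.3 to 0.7), and a baseline gap g of 0.2, 0.3 or 0.5 SD.

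**Standard errors (SD units).**
- t-test on 6-month scores: √(1/40 + 1/30) = 0.2415, 68 df.
- t-test on changes: 0.2415 × √(2(1 − ρ)) = 0.2415 × 0.894 = 0.216, 68 df.
- Regression on baseline: 0.2415 × √(1 − ρ²) = 0.2415 × 0.8 = 0.193, 67 df, multiplied by √(1 + g² × 40 × 30 / 70²) = 1.005, 1.011 or 1.030 for the three gaps.

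**Bias when there is no treatment effect.**
- Gap regresses to the mean (6-month gap = ρg): 6-month t-test ρg; change t-test (ρ − 1)g, the opposite sign; regression 0.
- Gap is stable (6-month gap = g): 6-month t-test g; change t-test 0; regression (1 − ρ)g.

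Example at g = 0.5: the 6-month t-test has bias 0.6 × 0.5 = 0.30 and 0.30 / 0.2415 = 1.24 standard errors; the change t-test has bias −0.20 and −0.20 / 0.216 = −0.93. The noncentral t distribution turns these ratios into rejection rates:

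| ρ = 0.6, no true effect | g = 0.2 | g = 0.3 | g = 0.5 |
|---|---|---|---|
| Regressing gap: 6-month t-test | 7.8% | 11.4% | 23.2% |
| Regressing gap: change t-test | 6.5% | 8.5% | 15.0% |
| Regressing gap: regression | about 5% | about 5% | about 5% |
| Stable gap: 6-month t-test | 12.9% | 23.2% | 53.2% |
| Stable gap: change t-test | 5% | 5% | 5% |
| Stable gap: regression | 6.9% | 9.3% | 16.8% |

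A simulation of 100,000 trials under the regressing gap gave 7.9%, 11.3% and 23.0% for the 6-month t-test and 5.1%, 4.9% and 5.1% for the regression. Over ρ from 0.3 to 0.7, the 6-month t-test in that case runs 6–9%, 7–14% and 9–30%.

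**Power.** True benefit 0.5 SD, ρ = 0.6, regressing gap of 0.3 SD against the trial group: the 6-month t-test falls from 53% to 26%, the change t-test rises from 63% to 81% (because its bias favours the trial group), and the regression goes from 72% to 71%.

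**Precision with no gap.** The difference detectable with 80% power is 0.686 SD for the 6-month t-test and 0.549 SD for the regression at ρ = 0.6.

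**The case against.** The strongest reply is that little rests on this comparison. The study is for feasibility, its success rule and sizing are single-arm and within-patient, the control number is only anticipated, and a covariate-adjusted regression is already planned. That stands and limits the severity. It does not dispose of the point. Sections 1.1 and the Schema still state a hypothesis to be tested against controls, and Section 9.3 disclaims formal conclusions for the PSA-failure comparison while Section 9.1 makes no such disclaimer for HRQOL.

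A reader might infer that the t-test must be on 6-month scores, so that the error has a known direction. The documents do not support that. The endpoint wording points that way, but Section 2.2 hypothesises less decline, Section 9.1 speaks of changes in quality of life, and Section 9.2 defines success by decline. On the change reading, the bias reverses under a regressing gap.

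A reader might also infer that adjusting for baseline restores the 5% level. It does so only if the gap regresses to the mean. With self- or physician-selected groups a stable difference is equally possible; the regression is then biased and the change-score t-test is not. The case for regression is therefore narrower. In both scenarios it is less biased than the 6-month t-test. Its worst-case bias equals that of the change score in size, (1 − ρ)g, with a smaller standard error (0.193 against 0.216).

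**Conclusion.** The point holds as a gap in specification with a real consequence: the primary between-group comparison has no designated analysis, no defined score and no named covariates, although baseline score is collected in both groups. Under the stated assumptions, the choice moves the false-positive rate between about 5% and 23% with a regressing gap of up to 0.5 SD, and between 5% and 53% with a stable one. The omission is certain from the text. The size and direction of its effect are not, because alpha, correlation, gap and the form of the gap are all assumed.

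It should be fixed, at modest severity. The Schema lists domains differently ("Patient reported data will be grouped into summary scores in each relevant quality of life domain (sexual, urinary, bowel, hormonal/vitality") from Section 9.1, which has fatigue and global quality of life in place of urinary and bowel. A reader might count that mismatch as further evidence here; it is a separate consistency point and adds no weight.

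**What to change.** In Section 9.1 and the Schema, state that the primary between-group analysis is a linear regression of the 6-month score on group and the patient's own baseline score in the same domain, reported as an adjusted difference with a 95% confidence interval. Keep the t-test as descriptive and say whether it uses 6-month scores or changes.

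Hormonal/vitality is the natural lead domain: Section 9.2 defines success on it, and Appendix B, which carries it, is scheduled at baseline and 6 months in both groups. The other domains and the composite would be supportive. Appendix B includes breast items among the hormonal questions, so state whether they count in the lead score; leaving them out would match the composite in Section 9.1.

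Age, Charlson score and risk group are optional, and should be named now if used. State that adjustment reduces but does not remove confounding from non-random allocation.

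The cost is wording; no patients, visits or forms are added. With baseline score alone, a gap of 0.2, 0.3 or 0.5 SD widens the standard error by 0.5%, 1.1% or 3.0%. The three extra covariates could cost about 0.01–0.06 SD of detectable difference at correlation 0.6 if they are imbalanced and not prognostic. At correlation 0.3, with a tenth of the variation in group explained by the covariates, that larger model is slightly less precise than the t-test (0.691 against 0.686 SD).
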